2.10.2 Adverse events (AEs)

The reporting of AEs and AEs of special interest will be reported in the following periods based on the treatment received as follows:

- For patients receiving EPO during the first 12 weeks and for those continuing with EPO after 12 weeks (no switching to EPO+DFX arm), the safety data will be reported based on the corresponding treatment group: EPO. The safety data will be reported in period 1-12 weeks, 13-24 weeks and 1-24 weeks.
- For patients receiving EPO+DFX DT or EPO+DFX FCT from week 1 and continuing with EPO+DFX DT or EPO+DFX FCT after 12 weeks or with DFX DT or DFX FCT alone after 12 weeks, the safety data will be reported based on the corresponding treatment group EPO+DFX. The safety data will be reported in period 1-12 weeks and 1-24 weeks.
- For patients receiving EPO alone and switched to EPO+DFX after 12 weeks of treatment, the safety data will be reported only in period 13-24 weeks.

Overall summary will be reported for AEs occurred in period 1-12 weeks of treatments and 1-24 weeks for patients receiving EPO alone and patients receiving EPO+DFX DT or EPO+DFX FCT.

Overall summary, SAE and AEs leading to study drug discontinuation will be reported for in the corresponding treatment: EPO, DFX DT, DFX FCT, EPO+DFX DT and EPO+DFX FCT.

All AEs will be coded using the latest version of MedDRA at the time of analyzing data using the Safety Set. The severities of the AE will be coded as mild/moderate/severe as documented in the CRF.

Summary tables for AEs have to include only AEs that started or worsened during the on-study period, the treatment-emergent AEs, i.e. TEAEs. However, all safety data (including

those from the pre and post-study periods) will be listed and those collected during the pre-study and post-study period will be flagged.

If an AE deteriorates or improves over time, new event will be reported accordingly with new severity.

The incidence of treatment-emergent AEs (new or worsening from baseline) will be summarized by system organ class and or preferred term, severity (mild/moderate/severe), type of AE and relation to study treatment.

Deaths reportable as SAEs and non-fatal serious AEs will be listed by patients and tabulated by type of AE.

Additionally, AEs and SAEs with suspected relationship to study drug, requiring dose adjustment, leading to drug interruption/discontinuation, requiring significant additional therapy will be specifically tabulated and listed.

AEs of special interest (AESIs) will be listed and summarized by grouped term and preferred term as shown in: [REDACTED]. It should be noted that this is a live document and may get updated with time and only the latest updated version should be used during the time of analyzing the data.

Also the AESI list to be used should have been updated based on the latest version of the case retrieval sheet (CRS) in terms of using the updated MedDRA version for identifying the AEs.

As mentioned above only the most recent version of the AESI list and CRS will be used for this study. AEs of special interest (AESIs) will be listed and summarized by group term and preferred term.

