	Hb increased < 1 g/dL from baseline and Hb < 12 g/dL	Increase EPO to 60,000 units/week *
	Hb increase is ≥ 1 g/dL and Hb < 12 g/dL	Continue EPO 40,000 units/week *
	Hb increase is ≥ 1 g/dL and Hb ≥ 12 g/dL	Hold EPO treatment *
Week 12	Hemoglobin status	Action
	Hb increased < 1 g/dL from baseline and Hb < 12 g/dL	If patient is in the combination arm: Discontinue from the study or If patient is in the EPO monotherapy arm: Switch to the combination EPO + DFX
	Hb increase is ≥ 1 g/dL and Hb < 12 g/dL	Continue current EPO dose *
	Hb increase is ≥ 1 g/dL and Hb ≥ 12 g/dL	Hold EPO treatment *

* Patients in combination arm will continue DFX DT 10 mg/kg/day or DFX FCT 7 mg/kg/day treatment

[figure not shown]
The primary objective (erythroid response according to IWG criteria: Hb increase ≥ 1.5 g/dL) will be assessed at 12 weeks of treatment. At any time, if Hb ≥ 12 g/dL, EPO will be stopped until the end of study.

At 24 weeks, patients initially assigned to the combination therapy who showed Hb increase ≥ 1 g/dL at week 12 will be assessed for full hematological response according IWG criteria (Erythroid response: Hb increase from baseline ≥ 1.5 g/dL; Neutrophil response: increase from baseline of ≥ 100% and > 0.5 x 10⁹/L; Platelet response: increase from baseline of ≥ 30 x 10⁹/L). Patients initially treated with EPO alone and switched to the combination therapy with EPO and DFX after 12 weeks will be assessed for erythroid response according to IWG criteria after 24 weeks.

No RBC transfusions are allowed after randomization, as transfusions would affect the endpoints of the trial. Patients who are RBC transfusion dependent must not be enrolled in the study. RBC transfusion dependence is defined as more than 2 units RBC /4 weeks at any time during the last 12 week period prior to study entry (Gale 2011). Patients must be withdrawn from the study anytime when transfusion as rescue therapy is needed.

Safety assessments are routinely performed including collection of AEs, SAEs, vital signs, physical examination, ECG, hematological and biochemistry assessments.

Patients will continue therapy until disease progression or intolerable toxicity, patient decision or death, after 12 weeks of combination treatment without response or after 24 weeks treatment duration at which point an End of Treatment (EOT) Visit will be performed and the End of Treatment CRF page will be completed.

30 day follow-up

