10.8 Sample size calculation

This is a pilot study which plans to enroll approximately 60 patients considering site capabilities. The sample size in a pilot study is based on the pragmatics of recruitment and the necessities of examining feasibility (Leon et al, 2011). Hence no formal sample size calculation based on primary endpoint assumptions is performed.

However to give an idea regarding primary endpoint analysis, for a given number of 60 patients, under scenarios, where considering a minimal detectable differences of 20%, 30% and 40% assuming a reference response rate of 40% at 5% level of significance gives a 95% Agresti-Caffo confidence interval of (-0.04, 0.44), (0.068, 0.53) and (0.18, 0.62).

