1.1 Document content

[figure not shown]
This Report and Analysis Plan (RAP) module describes the planned statistical methods for all efficacy and safety analyses for phase II study CICL670A2421 which is an open-label, phase II, randomized, pilot study to assess the effect in term of erythroid improvement of deferasirox (DFX) combined with erythropoietin (EPO) compared to EPO alone in patients with low- and int-1-risk myelodysplastic syndrome (MDS).

It is structured as:

- A draft of Section 9.7 (Statistical methods planned in the protocol and determination of sample size)
- A draft of Appendix 16.1.7 and 16.1.9 (Documentation of statistical methods) of the CSR.

It is written in future tense. It will be reviewed and updated (including conversion to past tense) for entry into the clinical study report after the analysis has taken place.

The shells for the in-text tables and figures, post-text tables, figures and listings, and the table of contents will be in Module 7. Programming specifications, including derivations and imputation dates will be given in Module 8.

2 Clinical Study Report Section 9.7 - Statistical methods planned in the protocol and determination of sample size

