2.2 Data included in the analyses

Data will be collected on patients aged ≥ 18 years or older with low- and-int-1-risk MDS, randomized in 1:1 ratio to DFX+EPO or EPO alone. If after 12 weeks of treatment with EPO alone, Hb increase is < 1 g/dL and total Hb is < 12 g/dL, the patient will switch to combination therapy of EPO and DFX. The study treatment duration is 24 weeks.

As per the current protocol, no interim analysis is planned. All interim (if required) and final CSRs will have a documented medical review by [REDACTED].

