2.7.2 Dose exposure

For all analysis described in this section, the Safety Set will be used.

The dose exposure will be provided for both DFX and EPO in the following way:

- *For patients randomized to EPO and those who do not switch to combination after 12 weeks: Duration of exposure to EPO for 24 weeks.
- For patients randomized to EPO+DFX: Duration of exposure to EPO for 24 weeks (with suitable exposure categories described in RAP M7) and duration of exposure to DFX DT or DFX FCT for 24 weeks (duration unit expressed as number of days with suitable exposure categories described in RAP M7).
- For patients randomized to EPO and switched to combination after 12 weeks: Duration of exposure to EPO for 24 weeks and duration of exposure to DFX DT or DFX FCT for 12 weeks (week 13 to week 24).

Note: Patients randomized to EPO and switched to combination after 12 weeks, will not be counted in *. The patient population as described in * will be exclusively those patients who were randomized to EPO and remained in the EPO arm for 24 weeks.

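### As worded, the AE period rules in SAP 2.10.2 leave switchers' weeks on EPO alone, and combination patients who stop by week 12, out of tables they appear meant to be in

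*SAP*

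**What the plan says.** SAP 2.10.2 states that AEs, including those of special interest, are reported by period according to treatment received. It then gives three rules, which protocol 10.5.11.1 shares in substance.

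- **Rule 1, EPO.** It applies "For patients receiving EPO during the first 12 weeks and for those continuing with EPO after 12 weeks (no switching to EPO+DFX arm"; its bracket closes there. Periods: weeks 1-12, 13-24 and 1-24.
- **Rule 2, combination.** It applies to patients who start on the combination, under this condition: "and continuing with EPO+DFX DT or EPO+DFX FCT after 12 weeks or with DFX DT or DFX FCT alone after 12 weeks". Periods: weeks 1-12 and 1-24.
- **Rule 3, switchers.** For EPO patients who "switched to EPO+DFX after 12 weeks of treatment, the safety data will be reported only in period 13-24 weeks".

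The same section also plans an overall AE summary for weeks 1-12 and 1-24, for EPO-alone and EPO+DFX patients, with no condition about week 12. SAP 2.10 assigns every safety analysis to the Safety Set. SAP 2.3 defines that set by at least one dose and a post-baseline safety assessment, so reaching week 12 is not required.

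What happens at week 12 depends on hemoglobin. For the EPO arm, SAP 2.2 says: "Hb increase is < 1 g/dL and total Hb is < 12 g/dL, the patient will switch to combination therapy of EPO and DFX". Protocol Table 4-1 applies the same hemoglobin condition to both arms: "If patient is in the combination arm: Discontinue from the study or If patient is in the EPO monotherapy arm", with the EPO patient moving to the combination.

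**The concern.** Weeks 1-12 is the only stretch in which safety can be compared between the arms as randomised. After it, EPO patients with a poor hemoglobin response receive DFX, and combination patients with the same result leave. AE incidence is the endpoint for the tolerability objective (protocol Table 3-1), so these tables carry that comparison.

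If a programmer follows rules 2 and 3 word for word, neither weeks 1-12 column is a randomised arm. The EPO column loses patients because of their week-12 hemoglobin. The combination column loses patients for the same reason, and also those who stopped earlier for any cause. Both selections are made after randomisation. The combination loss carries into weeks 1-24, because rule 2 governs that column too.

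**Working it through.** The plan states no figure to reproduce: it gives no number of switchers or early stops, and no confidence limits for AEs. The check is therefore mainly textual, with an illustration of scale.

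**1. Who is covered, rule by rule**

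| Patient | Rules 1-3 read literally | Treatment received, Safety Set |
|---|---|---|
| EPO, never switches | weeks 1-12, 13-24, 1-24 (rule 1) | same |
| EPO, switches at week 12 | weeks 13-24 only (rule 3) | EPO in weeks 1-12, then shown after the switch |
| Combination, continues past week 12 | weeks 1-12, 1-24 (rule 2) | same |
| Combination, stops at or before week 12 | no rule applies | combination in weeks 1-12 and 1-24 |

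The second and fourth rows differ. For switchers there is a competing reading: the opening clause of rule 1 can include them for weeks 1-12. For early-stopping combination patients no rule offers one; only the Safety Set sentence and the overall summary bring them in.

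**2. Illustrative counts**

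Inputs: about 60 patients randomised 1:1, so 30 per arm. Protocol 10.8 sets its scenarios "assuming a reference response rate of 40% at 5% level of significance", with differences of 20, 30 and 40 points, which gives 60%, 70% or 80% on the combination. Assumption: every non-responder switches or stops at week 12, and nobody else does.

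- EPO: 30 × (1 − 0.40) = 18 left out, 12 remain.
- Combination: 30 × (1 − 0.60, 0.70, 0.80) = 12, 9 or 6 left out; 18, 21 or 24 remain.

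These are not ceilings. A response needs a gain of at least 1.5 g/dL, while the switch or stop needs a gain below 1 g/dL, so patients in between stay in. Against that, response counts at any time in the first 12 weeks, so a responder whose gain has fallen below 1 g/dL at week 12 can still switch or stop. Stops before week 12 would shrink the combination column further.

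**3. What the smaller columns can show**

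The two-sided 95% Clopper-Pearson upper limit after zero events is 1 − 0.025^(1/n).

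| Column | n | Upper limit |
|---|---|---|
| Full arm | 30 | 11.6% |
| EPO, planning rate | 12 | 26.5% |
| Combination, 60 / 70 / 80% | 18 / 21 / 24 | 18.5 / 16.1 / 14.2% |
| EPO, if 10 / 15 / 20 switch (assumed) | 20 / 15 / 10 | 16.8 / 21.8 / 30.8% |

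**4. Direction of any bias**

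Let f be the share of the EPO arm that switches, and pN and pS the weeks 1-12 AE rates in non-switchers and switchers. The literal column shows pN; the whole arm has (1 − f)pN + f·pS. The difference is f(pN − pS). With f = 18/30 = 0.6 and assumed rates:

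- pN = 20%, pS = 40%: the arm has 0.4 × 20 + 0.6 × 40 = 32%, the table shows 20%.
- pN = 40%, pS = 20%: the arm has 0.4 × 40 + 0.6 × 20 = 28%, the table shows 40%.
- pN = pS: no difference.

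Nothing in the documents fixes pN − pS, so the sign is open.

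**The case against.** The strongest reply is that the inclusive reading was intended all along. Rule 1 names two groups, and the first is redundant unless it includes later switchers. On that view, the restriction in rule 3 only means that switchers' combination data have no weeks 1-12 or 1-24 column. The protocol's summary of Amendment 2 says the text was added to explain safety reporting on both sides of the cross-over. The overall summary and the Safety Set sentence carry no week-12 condition. Where the SAP wants switchers left out it says so: in 2.7.2, "Patients randomized to EPO and switched to combination after 12 weeks, will not be counted in" the EPO-only exposure group. The layouts may also be right already: "The shells for the in-text tables and figures, post-text tables, figures and listings, and the table of contents will be in Module 7", and that module is not among the documents.

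Most of this stands as evidence of intent. It does not cure the wording. Rule 3 limits switchers' safety data as a whole, not just their combination data, and rule 2 makes continuation a condition. No sentence says which text prevails, so two programmers could build different tables.

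The reply is also right that the consequences are modest. The trial is an open-label pilot with descriptive AE tables. SAP 2.10.1 puts true and assigned treatment in every safety listing, and the by-treatment summaries of serious AEs and discontinuations state no exclusion. Listings, however, do not supply rates or denominators.

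**Conclusion.** Wrong as written, and minor. Rules 2 and 3 of SAP 2.10.2, and their counterparts in protocol 10.5.11.1, do not deliver the treatment-received, Safety Set reporting that the rest of the plan points to. The effect is confined to descriptive AE period tables. The illustrative counts rest on 30 per arm and the planning response rates, and are not bounds.

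Four stronger inferences are not supported:

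- **The sponsor has decided to drop these patients.** The surrounding text points the other way, and the shells are unseen.
- **The EPO column would contain only responders.** Notes in SAP 2.9.2.4 and 2.9.2.5 describe non-switchers that way, but a gain of at least 1 and below 1.5 g/dL avoids the switch without meeting the response criterion.
- **AE data are lost.** They remain in the listings with true treatment.
- **The tables would favour one arm.** The bias may run either way or be zero.

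One separate inconsistency is plain. Code S01 in SAP Table 4-7 concerns patients never exposed to study medication, and its action keeps them in the Safety Set, although SAP 2.3 requires at least one dose. It does not add to the weight of this point.

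**What to change.** 1. In rule 2 of SAP 2.10.2, replace the continuation condition with: *all Safety Set patients who start on EPO+DFX, including those who stop at or before week 12, are counted under EPO+DFX for weeks 1-12 and weeks 1-24.* Changing rule 3 alone would leave the present rule 2 wording in conflict with it.
2. Replace rule 3 with: *EPO patients who switch are counted under EPO for weeks 1-12, and shown separately as EPO then DFX+EPO for weeks 13-24.*
3. Check that the Module 7 shells match.
4. Align protocol 10.5.11.1 at the next amendment. Protocol 12.1 requires a written, approved amendment for any change, so until then the SAP should record the new wording as a clarification.
5. As a separate correction, change the S01 action in Table 4-7 to inclusion in the FAS and exclusion from the Safety Set.

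The cost is two reworded SAP rules, one table cell and a shell check. No new data are needed, and no treatment rule changes.

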10.5.11.2 Adverse events (AEs)

Summary tables for adverse events (AEs) will include only AEs that started or worsened during the on-treatment period, the **treatment-emergent** AEs. However, all safety data (including those from the pre and post-treatment periods) will be listed and those collected during the pre-treatment and post-treatment period are to be flagged.

[figure not shown]
The incidence of treatment-emergent adverse events (new or worsening from baseline) will be summarized by system organ class and or preferred term, severity (mild/moderate/severe), type of adverse event, relation to study treatment by treatment group.

Deaths reportable as SAEs and non-fatal serious adverse events will be listed by patients and tabulated by type of adverse event and treatment group.

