2.10.1 Analysis set and grouping for the analyses

The overall study period will be divided into three mutually exclusive segments:

1. pre-treatment period: from day of patient's informed consent to the day before first dose of study medication

2. on-treatment period: from the day of first dose of study medication to 30 days after last dose of study medication
3. Post-treatment period: starting at day 31 after last dose of study medication.

If dates are incomplete in a way that clear assignment to pre-, on-, post-treatment period cannot be made, then the respective data will be assigned to the on-treatment period.

The assessment of safety will be based mainly on frequency of AEs and on the number of laboratory values that fall outside of pre-determined ranges.

The safety summary tables will include on-study assessments (with the exception being the prior concomitant medications, laboratory parameters with baseline value taken prior to start of study drug). All safety assessments will be listed and those collected outside of the on-study period will be flagged appropriately.

In all safety listings, a column will be added to provide the true treatment (EPO alone, EPO+DFX DT or EPO+DFX FCT, DFX DT or DFX FCT alone, no treatment) at onset of AE or at time of any other safety assessment and the original treatment assigned.

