4.2.9 Baseline

In general, for safety variables, the baseline value is defined to be the last available value prior to or on the day of first dose of study drug. For efficacy variables, the baseline value is defined to be the last available value prior to or on the day of randomization.

This definition does not apply for the following exceptions, where a specific definition was used:

- Serum creatinine: baseline value is defined as the mean of visit 1 and 2.
- Serum ferritin: baseline value is defined as the mean of visit 1 and 2.

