	AEM MISSING	AEM < TRTM	AEM = TRTM	AEM > TRTM
AEY MISSING	NC Uncertain	NC Uncertain	NC Uncertain	NC Uncertain
AEY < TRTY	(D) Before TRTSTD	(C) Before TRTSTD	(C) Before TRTSTD	(C) Before TRTSTD
AEY = TRTY	(B) Uncertain	(C) Before TRTSTD	(B) Uncertain	(A) After TRTSTD
AEY > TRTY	(E) After TRTSTD	(A) After TRTSTD	(A) After TRTSTD	(A) After TRTSTD

The legend to the above table is shown in Table 4-4.

Table 4-4 Relationship and Imputation Legend

Relationship	
Before TRTSTD	Indicates AE start date prior to Treatment Start Date
After TRTSTD	Indicates AE start date after Treatment Start Date
Uncertain	Insufficient to determine the relationship of AE start date to Treatment Start Date
Imputation Calculation	
NC / Blank	No convention/imputation
(A)	01MONYYYY
(B)	TRTSTD+1
(C)	15MONYYYY
(D)	01JULYYYY
(E)	01JANYYYY

Few examples are shown in Table 4-5.

Table 4-5 Example Scenarios

Partial AE start date	Treatment start date	Relationship	Imputation Calculation	Imputed Date
12mmyyyy	20OCT2001	Uncertain	NC	<blank>
ddmmm2000	20OCT2001	Before	(D)	01JUL2000
ddmmm2002	20OCT2001	After	(E)	01JAN2002
ddmmm2001	20OCT2001	Uncertain	(B)	21OCT2001
ddSEP2001	20OCT2001	Before	(C)	15SEP2001
ddOCT2001	20OCT2001	Uncertain	(B)	21OCT2001
ddNOV2001	20OCT2001	After	(A)	01NOV2001

For any continuing events (e.g. AEs, concomitant medication, etc) which needs to be summarized for annual reports (or any interim analyses), when a date cut-off date is used an indication in the listings will be done to inform that the event is continuing. For patients who discontinue the study with ongoing events, the discontinuation date will be used as the completion date of the event.

Vital sign, Study Completion, CMP, ECG and laboratory assessment dates will be imputed in associating visit date from Visit-based event date imputation (AVIS) (see RAP Module 8).

Any event which has a partial date and requires imputing but has no specific imputation rule will be described in the RAP Module 8 and the imputed will be as follows:

- If the day and month is missing, it will be replaced by 1st of July. If only the day is missing it will be replaced by the 1st of that month. Partial dates will remain partial in the data listings.
- Missing day information for start date of prior chelation therapy or start date of history of blood transfusions will be imputed by the 15th of the Month. If the month will be missing it will be imputed by July.

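### An AE that began on EPO alone and eases after the switch can be counted as a new event under EPO+DFX in weeks 13–24, because SAP 2.10.2 opens a new record on improvement and does not link it to the original

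*SAP*

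**What the plan says.** SAP 2.10.2 gives the recording rule: "If an AE deteriorates or improves over time, new event will be reported accordingly with new severity". The same section states the treatment-emergent test twice: "Summary tables for AEs have to include only AEs that started or worsened during the on-study period, the treatment-emergent AEs, i.e. TEAEs", and "The incidence of treatment-emergent AEs (new or worsening from baseline) will be summarized by system organ class". Protocol 10.5.11.2 agrees; its tables "will include only AEs that started or worsened during the on-treatment period".

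Two definitions fix the reference point. SAP 2.10.1 sets the "on-treatment period: from the day of first dose of study medication to 30 days after last dose of study medication". SAP 4.2.9 gives the general rule on the safety side: "the baseline value is defined to be the last available value prior to or on the day of first dose of study drug". Neither restarts when DFX is added at the switch.

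SAP 2.10.2 and Protocol 10.5.11.1 report patients who switch from EPO to EPO+DFX for weeks 13–24 only. SAP 2.10.2.1 counts patients, not records: repeated AEs with one preferred term are shown at the greatest severity, and a patient counts once per system organ class. SAP 2.10.1 adds a listing column with the actual treatment at AE onset and the assigned treatment.

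Protocol 8.1.1 asks sites to record AEs that begin or get worse after consent, and to follow each one to resolution with severity reassessed at visits. It does not ask for a new AE when an existing one eases.

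**The concern.** A fall in severity is not a new harm, yet the recording rule gives it a new event with its own start date. If that date decides the reporting period, the event belongs to whatever treatment the patient is on when the AE gets better.

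This matters most for switchers. AE incidence is a stated safety endpoint (Protocol Table 3-1), and the weeks 13–24 table is the planned summary of switchers' AEs on the combination. An AE that arose on EPO alone could appear there as an event on EPO+DFX, with nothing in the table to show that it was an improvement.

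**Working it through.** The plan gives no figure to reproduce here, so the check applies its rules to three illustrative record patterns.

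**Inputs.** Periods are from SAP 2.10.2: weeks 1–12 are days 1–84 (12 × 7), and weeks 13–24 start on day 85. Counting follows SAP 2.10.2.1. The days of onset and easing are made up for illustration.

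**Three readings of a record opened because severity changed**
- (i) The record's own start date decides whether and where it counts.
- (ii) It counts only if its severity exceeds the severity before the first dose of study drug.
- (iii) It is linked to the original AE, and a fall in severity is not a new onset.

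| Case | Records | Table | (i) | (ii) | (iii) |
|---|---|---|---|---|---|
| A: screening AE eases | moderate day −5, mild day 20 | weeks 1–12 | 1, mild | 0 | 0 |
| B: starts and eases in one period | severe day 10, mild day 30 | weeks 1–12 | 1, severe | 1, severe | 1, severe |
| C: EPO-phase AE eases after switch on day 85 | severe day 60, mild day 100 | weeks 13–24 | 1, mild | 1, mild | 0 |

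**Case A** depends on the reading. A new event dated on treatment has started on treatment; compared with baseline, it has not worsened. The SAP does not say which test prevails.

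**Case B** is unaffected. The count-once and greatest-severity rules give the same patient count and maximum severity under all readings. Only record counts and listings grow.

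**Case C** is counted under (i) and also under (ii). The AE was absent before EPO, so any severity exceeds the pre-dose baseline. The greatest-severity rule does not help, because the severe record lies in weeks 1–12, outside the table. The AE enters at the milder grade. Only linking removes it.

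**Size.** SAP 2.11 plans about 60 patients, and Protocol 4.1 randomises 1:1: 60 / 2 = 30 on EPO alone. With the 40% reference response rate in SAP 2.11, 30 × 0.40 = 12 respond and 30 − 12 = 18 do not. Treating responders as non-switchers and ignoring dropout, 18 is about the most that could switch. Fewer may do so, because switching needs an Hb rise below 1 g/dL while response needs at least 1.5 g/dL, so patients in between do neither.

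One misplaced patient adds 100/n points to the incidence of that preferred term:
- n = 18: 100/18 = 5.6
- n = 12: 100/12 = 8.3
- n = 9: 100/9 = 11.1
- n = 6: 100/6 = 16.7

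This applies if the patient has no other qualifying record of the same term in weeks 13–24.

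**The case against.** The strongest reply is that the SAP never says an improvement is treatment-emergent. A reader might infer from the recording rule that every AE easing on treatment is tabulated as treatment-emergent. The documents do not support that: both SAP tests, and the protocol's, can be read to exclude a screening-phase AE that only got milder. This stands for case A, which is an unresolved conflict in the text. It does not answer case C, where the baseline precedes EPO.

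A reader might also infer that each improvement record adds one false event. SAP 2.10.2.1 rules that out for patient incidence within a reporting period. Nor does the switch problem bias the randomised comparison, since weeks 1–12 contain no switch. Screening-phase carry-over, if counted, falls under the same rule in both arms.

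Frequency is also open. Protocol 8.1.1 asks for no new record on improvement, so sites may seldom create one. The programming specifications (Module 8, named in SAP 1.1) were not available and may contain a linking rule. The listing column lets individual cases be traced. These points limit the size but do not supply the missing rule.

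A further tempting inference is that the partial-date rules in SAP 4.3 wrongly remove AEs from DFX in the switch month. There, an AE with a missing day in a month after the first-dose month is set to the 1st (rule A). The first-dose month, whose label means "Insufficient to determine the relationship of AE start date to Treatment Start Date", uses the start date plus one day (rule B). Suppose DFX starts on day k of a 30-day month and onset is uniform. Then (31 − k)/30 of such AEs truly begin on or after DFX start, on average 15.5/30 = 52%, and rule A dates all of them before it unless k = 1. Dating them to DFX start plus one day instead would misplace (k − 1)/30, on average 14.5/30 = 48%. Since rule A misplaces none at k = 1, its average error is also (465 − 30)/900 = 48%. The change only reverses the direction. SAP 4.3 also sends partial dates back to the investigator for resolution. This is a choice of convention, not a defect.

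**Conclusion.** The point holds for switchers. Following SAP 2.10.2 literally, an AE that began on EPO alone and eases after the switch counts as a new event under EPO+DFX in weeks 13–24. Neither the baseline qualifier nor the counting rules remove it. This assumes that the new record's start date sets the reporting period, which the treatment-at-onset listing column implies but the SAP does not state.

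One such patient moves a term's incidence by 5.6 to 16.7 points over the assumed 18 to 6 switchers. The number of such patients cannot be known from the documents and is probably small. For screening-phase AEs that ease on treatment the SAP is ambiguous.

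Severity is minor: the tables are descriptive, the study is a pilot, and the affected group is small and non-randomised. It still deserves correction, because a stated rule, followed as written, gives a wrong switcher incidence.

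**What to change.** In SAP 2.10.2, add:
- A record opened only because severity fell is linked to the original onset and is not counted as a new or treatment-emergent event.
- Treatment-emergent status and reporting period follow the original onset or a true worsening.
- For switchers, worsening in weeks 13–24 is judged against the last severity recorded before the first DFX dose.

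Align the recording rule with Protocol 8.1.1, and carry the linking rule into Module 8 if it is not already there. The cost is a linking flag and slightly more programming; no new data are needed.

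No change to the partial-date rules is required. If the sponsor wants the switch month handled like the first-dose month, applying rule B to the DFX start date is an optional convention.
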